2.2 SECONDARY

1. To estimate objective response rate to combination AVB-S6-500 and durvalumab therapy
2. To estimate the median immune-related progression free survival (irPFS) as well as overall survival OS by RECIST 1.1 after treatment with combination durvalumab and AVB-S6-500
3. To investigate molecular and immunological changes associated with the combination of AVB-S6-500 and durvalumab; specifically to describe changes in T cell populations (including but not limited to CD3, CD8, CD4, FOXP3) and cell proliferation, as well as report changes in the proportion of macrophage phenotypes M1 and M2 (with phenotypic markers potentially including arginase1, CD11b, PDL-1, and CD206)

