3.1 END OF STUDY ENROLLMENT

In the first quarter of 2021, study supporters Aravive and AstraZeneca made the decision to end enrollment based on available data after the 5th evaluable subject completed treatment on the safety lead-in.

[figure not shown]

Figure 2. Study Schema

Dosing schedule as above demonstrates investigational product at week of administration, where A = AVB-S6-500 monotherapy, D= durvalumab monotherapy, and A+D = AVB-S6-500 + durvalumab combination therapy

* Patients receiving the recommended Phase 2 dose (RP2D) will then be included in the primary analysis of the combination therapy. However, these patients will continue on the Safety Lead-in dosing schedule and will not participate in the Phase 2 monotherapy. See de-escalation dosing regimens below.

† Sample size calculations account for predicted 8% dropout rate due to toxicity.

‡ Dosing schedule shown reflects the starting dose for the dose escalation. This may be adjusted for the de-escalation schedule below and determination of the RP2D.

Table 1. Dosing for Dose Escalation

Dose Level	Durvalumab + AVB-S6-500
Dose Level 0 (Initial dose)	durvalumab (1500mg Q4W), AVB-S6-500 (10mg/kg Q2W)
Dose level 1	durvalumab (1500mg Q4W), AVB-S6-500 (15mg/kg Q2W)
Dose level 2	durvalumab (1500mg Q4W), AVB-S6-500 (20mg/kg Q2W)

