3.2 SAFETY LEAD-IN

The trial will begin with a dose escalation phase to determine the recommended Phase 2 dose (RP2D). The design for dose escalation is provided in **Section 9**. The dose level established in the dose escalation phase will define the recommended dosing for subsequent combination treatment. Those patients treated at the RP2D will continue on treatment and will contribute to primary analysis of combination therapy.

Of note, prior to receipt of any treatment, all patients will undergo a computed tomography (CT) scan to determine baseline volume of disease. An initial pre-treatment biopsy and blood samples will be obtained to measure immune function in both the pretreated tumor environment and systemically.

To investigate translational aims, all patients participating in safety lead-in cohorts will undergo a biopsy and blood sampling after receiving 6 weeks of treatment.

Refer to the Schedule of Assessments in **Table 6** for complete details (**Section 6.5**).

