^o Resting 12-lead ECG on which QTcF must be < 470 ms. ECGs should be obtained after the patient has been in a supine position for 5 minutes and recorded while the patient remains in that position. In case of clinically significant ECG abnormalities, including a QTcF value > 470 ms, 2 additional 12-lead ECGs should be obtained over a brief period (e.g., 30 minutes) to confirm the finding. ECGs may be performed more frequently than noted in the schedule if clinically indicated.

^p Imaging to occur Q8W (± 7 days) and should continue unless the subject has confirmed progression, death or unacceptable toxicity. If progression is identified, then a confirmatory scan should be obtained 6 weeks (± 7 days) after the first positive scan. As long as treatment is being well-tolerated and the investigator believes that the patient may derive benefit, the patient should continue regularly scheduled visits and receive additional treatment until the confirmatory scan results have been reviewed.

^q Patients with suspected brain metastases at screening should have an MRI (preferred) or CT each preferably with intravenous (IV) contrast of the brain.

^r To occur during the final week of the marked Cycle, prior to initiating treatment in the following Cycle.

^s RECIST measurements will be performed in line with imaging. Refer to **Section 7.1**.

^t Refer to **Section 6.6.2** for details regarding Tumor sample.

^u Biopsy can be newly acquired or archival ≤ 3 years old. Refer to **Section 6.6.2** for details regarding tumor sample.

^v If subjects are not required to have a diagnostic biopsy (i.e. tumor recurrence/progression has been already histologically confirmed), tissue acquisition will occur during a research-only biopsy procedure. Refer to **Section 6.6.2** for details regarding tumor sample.

^w To occur immediately prior to Cycle 3 where possible. Refer to **Section 6.6.2** for details regarding tumor sample.

^x Sample will be taken within 45 minutes before dosing. Additional post-dose time points will be collected only on Day 1 of Cycle 1. See note “y” below. Refer to **Section 6.6.1**. A blood sample will be collected and processed for serum at the 90-day follow up visit to analyze for the presence of anti-drug antibodies for AVB-S6-500.

^y Samples will be taken within 45 minutes before dosing begins and at 1 and 4 hours after the completion of treatment. Refer to **Section 6.6.1**.

^z Cycles 3 and 4 only.

^{aa} Refer to **Section 5.2**.

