6.6.2 TUMOR BIOPSIES

Pre- and on-treatment biopsies will be performed as part of this clinical investigation. To avoid putting patients in undue risk, procedures more invasive than a core biopsy will not be used. Pretreatment biopsies will be collected prior to the first dose of study drug regimen. On-treatment biopsies include sampling after monotherapy treatment and then after combination treatment with Durvalumab and AVB-

S6-500 when there is a lesion amenable to biopsy as assessed by imaging study by MDACC Radiologist. The time points for each Phase and Arm are noted in the Schedules of Assessments in **Section 6.5**.

When possible, on-treatment biopsies will be obtained from the same area of tumor as the pre-treatment biopsy.

At all biopsy time points and when deemed clinically safe, up to 10 core biopsies will be collected by Radiology faculty through an image-guided procedure. When feasible and depending on the tumor volume, 1-3 cores will be processed as formalin-fixed, paraffin-embedded blocks (FFPE) and 1-3 cores will be flash frozen, and remaining cores will be kept fresh in media. In cases where only limited amounts of tumor can be obtained, the FFPE samples will be prioritized. Samples will be collected, labeled, processed, and stored by the MDACC Gynecologic Oncology Tumor Bank. Sample identification and associated collection data will be entered into a secure database.

Translational studies including tumor immune and gene expression profiling will be performed with collaborators at MD Anderson group and Discovery Life Sciences (DLS). This assessment may include, but is not limited to, fresh flow cytometry, tissue cyTOF, and multiplex immunofluorescence. Exploratory analyses may include sequencing platforms and, given that assays for these evaluations are rapidly evolving in the laboratories at MDACC, other assays will be performed with the current state of the art technology available at the time of analysis. Aliquots may be stored and used for exploratory and future translational immunology research.

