9.2 METHODS OF STATISTICAL ANALYSES

We will use descriptive statistics to summarize the demographic and clinical characteristics of the subjects. We will estimate the objective response rate (ORR) along with a 90% confidence interval. Response is defined in **Section 7.2**. We will estimate the median immune-related progression free survival (irPFS) after treatment with combination durvalumab and AVB-S6-500 using the product-limit estimator of Kaplan and Meier. When appropriate, we will model irPFS using Cox proportional hazards regression as an exploratory analysis because of the small sample size. Immune-related PFS is defined as the time from the date of dual therapy treatment initiation to the date of initial radiologic evidence of progressive disease (**Section 7.2**) or death. Those who are immune-related progression-free and alive will have irPFS censored at their last clinic visit.

Molecular and immunological changes will be summarized with standard descriptive statistics. Changes in T cell populations and proliferation will be calculated along with 95% confidence intervals and compared between pre and posttreatment biopsies using two sample t-test. Similar summaries will be used to compare proportions of macrophage phenotypes. We will tabulate adverse events by grade, and by relationship to study drug. We will estimate the proportion of subjects that discontinue treatment due to adverse events with 90% confidence intervals. We will estimate the unacceptable toxicity rate with a 90% confidence interval.

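### Section 9.2 compares pre- and post-treatment biopsies from the same patients with a two-sample t-test, so the pairing is ignored and the true level depends on an unstated within-patient correlation

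*Combined protocol and SAP*

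**What the plan says.** Section 9.2 of the combined protocol and SAP plans to calculate changes in T-cell populations and proliferation with 95% confidence intervals. These measures are to be "compared between pre and posttreatment biopsies using two sample t-test". Macrophage phenotype proportions are to be handled with similar summaries.

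The analysis serves the third secondary objective in Section 2.2, which is "specifically to describe changes in T cell populations" and related markers.

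The sampling plan is as follows.

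- Section 3.2, before treatment: "An initial pre-treatment biopsy and blood samples will be obtained".
- Section 3.2, on treatment: "all patients participating in safety lead-in cohorts will undergo a biopsy and blood sampling after receiving 6 weeks of treatment".
- Section 6.6.2, site: "When possible, on-treatment biopsies will be obtained from the same area of tumor as the pre-treatment biopsy".
- Section 6.6.2, condition for an on-treatment biopsy: "when there is a lesion amenable to biopsy as assessed by imaging study".
- Section 6.5, Table 6 footnotes: Screening 1 tissue may be new, or archival up to 3 years old. At Screening 2, where no diagnostic biopsy is required, "tissue acquisition will occur during a research-only biopsy procedure".

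Section 3.1 records the decision to "end enrollment based on available data after the 5th evaluable subject completed treatment on the safety lead-in".

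**The concern.** Each patient with both biopsies contributes one pair of values. A two-sample t-test treats the two sets as independent groups. It therefore omits the covariance between a patient's two samples, and it refers the statistic to 2n - 2 degrees of freedom when there are only n independent units.

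Loose wording is an unlikely explanation. Section 9.2.2 uses the same test name to compare the two monotherapy arms, where independent groups is the right assumption. No paired t-test, signed-rank test or mixed model is named anywhere in the document.

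At stake is the p-value attached to the T-cell change. With positive correlation and equal variances the test rejects too rarely and can miss a real within-patient change. With negative correlation it rejects too often. This is not a general claim of inflated false positives.

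**Working it through.** **What the documents supply.** The test, the 95% confidence level and the paired sampling plan are stated. No significance level is given for this test; two-sided 5% is taken to match the 95% interval. The plan gives no SD, correlation, expected change, power or number of complete pairs for this comparison, so there is no figure of its own to reproduce. Those quantities are assumed below and shown over a range.

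**Why the level moves.** Let n be the number of pairs, s1 and s2 the pre and post SDs, and rho the within-patient correlation.

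- True variance of the mean change: (s1² + s2² - 2·rho·s1·s2)/n.
- Variance targeted by the two-sample test: (s1² + s2²)/n.

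With s1 = s2 the ratio of true to assumed variance is 1 - rho. In large samples the true level of a nominal 5% test is 2·[1 - Φ(1.96/√(1 - rho))]:

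- rho = -0.3: 1.96/√1.3 = 1.72, level 8.6%
- rho = 0: 1.96, level 5.0%
- rho = 0.3: 1.96/√0.7 = 2.34, level 1.9%
- rho = 0.5: 1.96/√0.5 = 2.77, level 0.6%
- rho = 0.7: 1.96/√0.3 = 3.58, level 0.03%

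**Small samples.** Bivariate normal data were simulated with 400,000 replicates per cell (simulation error about 0.03 percentage points at 5%). The pooled two-sample t on 2n - 2 degrees of freedom was compared with the paired t on n - 1. For 5 pairs (8 against 4 degrees of freedom), equal variances:

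| rho | Two-sample size | Paired size | Coverage of a 95% CI with the two-sample SE | Power for a 1-SD change, two-sample | Power for a 1-SD change, paired |
|---|---|---|---|---|---|
| -0.3 | 8.0% | about 5% | 92.0% | 31% | 19% |
| 0 | 5.0% | about 5% | 95.0% | 29% | 23% |
| 0.3 | 2.7% | about 5% | 97.3% | 26% | 31% |
| 0.5 | 1.4% | about 5% | 98.6% | 25% | 40% |
| 0.7 | 0.5% | about 5% | 99.5% | 24% | 59% |

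The coverage column applies only if the interval is built on the two-sample standard error. Section 9.2 does not say how it is built.

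**Other numbers of pairs.** For 3, 5 and 8 pairs the two-sample size is 7.4%, 8.0% and 8.3% at rho = -0.3, and 2.1%, 1.4% and 1.1% at rho = 0.5. At rho = 0.5, power for a 1-SD change (two-sample against paired) is 13% against 18% with 3 pairs and 46% against 68% with 8.

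**Unequal variances, 5 pairs.** At a post/pre SD ratio of 3, the pooled test has size 6.1% at rho = 0.1 and 5.5% at rho = 0.2. At a ratio of 4 and rho = 0.3 it has 5.8%. The Welch version gives 4.8%, 4.3% and 4.3% in those three cells. So with strongly unequal variances the pooled test can slightly exceed 5% even under weak positive correlation.

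The paired test stayed at 4.9% to 5.1% in every setting.

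**The case against.** Four arguments can be made against acting on this.

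1. **Section 9.2 may no longer apply.** Section 9 says, just before the phase II randomization text, that what follows is kept for reference only, and it does not mark where that ends. This ambiguity stands. However, Section 9.2 and its subsections are where the adverse-event tabulation and the estimation of response rate and irPFS are set out; Section 11.1 adds only toxicity monitoring. If all of 9.2 had lapsed, the primary objective would have no stated analysis beyond that monitoring. The lead-in biopsies and the secondary objective they serve also remain.

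2. **Archival tissue weakens the pairing.** Older tissue, or tissue from another site, may lower the correlation, but it still belongs to the same patient.

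3. **The analysis is descriptive and very small.** This stands. Enrollment ended at the fifth evaluable lead-in subject, and an on-treatment biopsy depends on an accessible lesion, so there may be fewer than 5 complete pairs. No decision rests on the p-value.

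4. **The paired test can have less power.** This also stands when the correlation is near zero or negative. At 5 pairs it falls from 29% to 23% at rho = 0. It falls from 31% to 19% at rho = -0.3, but there the two-sample test is buying power with a size of 8.0%. At rho = 0.3 the gain is only from 26% to 31%.

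These arguments limit the consequence. None makes a two-sample test the right analysis for paired samples.

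**Conclusion.** The named test does not match the sampling plan. With equal variances it has its nominal level only if the within-patient correlation is zero. At 5 pairs the true size ranges from 8.0% to 0.5% over correlations from -0.3 to 0.7. The paired test holds about 5% across that range, and gains power clearly only from a correlation of about 0.5 upward.

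The mismatch itself is plain from the text. Its size rests on assumed normality, correlation, SD ratio, a 1-SD change and the number of complete pairs, none of which the documents give. The finding is confined to the named t-test, because the document leaves open how the 95% interval is formed and whether the macrophage summaries include a test. The severity is minor.

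**What to change.** In Section 9.2, replace the two-sample t-test for this comparison with the following: the mean within-patient change (post-treatment minus pre-treatment), its 95% confidence interval from the paired differences, and a paired t-test. Apply the same to macrophage proportions where they are compared before and after treatment.

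State which tissue is the pre-treatment value when a patient has both Screening 1 and Screening 2 samples. Present patients with only one biopsy descriptively. The two-sample test in Section 9.2.2 can stay for the between-arm comparison, which belongs to the original phase II design.

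The cost is a small text change in Section 9.2 and no new data. Patients missing one biopsy drop out of the test, and some power is lost if the correlation is near zero or negative.

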9.2.1 SAFETY ANALYSES

We will tabulate adverse events by grade, and relationship to study drug. We will estimate the proportion of subjects that discontinue treatment due to treatment-related adverse events with 90% confidence intervals. We will estimate the unacceptable toxicity rate with a 90% confidence interval.

9.2.2 EXPLORATORY ANALYSES

Two-sample t test or chi-squared test will be used to compare continuous and binary variables for molecular and immunologic differences between pre-treatment with single agent AVB-S6-500 as compared to durvalumab.

The maximum of 6 patients who enroll directly into the safety-lead in phase of combination therapy will be separately analyzed for exploratory outcomes of response rate to combination alone. Similarly, pretreatment monotherapy arms will be compared for safety and signal of monotherapy response, as well as for impact on subsequent response rate in combination treatment.

9.2.3 INTERIM ANALYSES

We will conduct an interim analysis for efficacy and safety once 12 subjects have been evaluated for dual therapy. As stated in Section 6.2, DLTs will be evaluated from the time of first drug administration until 6 weeks. ORR will be determined at 8-week scan, but as stated in Table 10, disease progression will require a confirmatory scan. Based on Table 10, we will stop the trial if 0 responses are detected or 6 or more toxicities are observed.

We simultaneously monitor efficacy and safety endpoints using the Bayesian optimal phase 2 (BOP2) design [63]. Specifically, let n denote the interim sample size and N denote the maximum sample size. Let Y_{eff} and Y_{tox} respectively denote the efficacy and toxic endpoints, with $Y_{eff} = 1$ and $Y_{tox} = 1$ respectively indicating that patients experience efficacy and toxicity. We assume that the joint distribution of (Y_{eff}, Y_{tox}) follows a multinomial distribution with 4 elementary outcomes: $(Y_{eff}, Y_{tox}) = (1, 1), (1, 0), (0, 1)$ and $(0, 0)$. Let $p_{eff} = Pr(Y_{eff} = 1)$ and $p_{tox} = Pr(Y_{tox} = 1)$. The treatment is deemed as unacceptable if $p_{eff} \leq 0.1$ or $p_{tox} > 0.4$. Thus, we will stop enrolling patients and claim that the treatment is unacceptable if

$$Pr(p_{eff} > 0.1 | data) < \lambda \left(\frac{n}{N}\right)^\alpha,$$

or

$$Pr(p_{tox} \leq 0.4 | data) < \lambda \left(\frac{n}{N}\right)^\alpha,$$

where $\lambda=0.65$ and $\alpha=0.9$ are design parameters optimized to maximize the probability of correctly concluding an efficacious and safe treatment as acceptable when $p_{eff} = 0.3$, $p_{tox} = 0.2$ and $p_{eff,tox} = 0.06$, while controlling that the probability of incorrectly claiming an ineffectual and toxic treatment, with $p_{eff} = 0.1$, $p_{tox} = 0.4$ and $p_{eff,tox} = 0.04$, as acceptable is less than 10%. Assuming a Dirichlet prior distribution $Dir(0.04, 0.06, 0.36, 0.54)$ for the treatment effect, the above decision rule corresponds to the following stopping boundaries and yields a statistical power of 0.9245 under H_1 :

Table 14. Optimized stopping boundaries

# patients treated	Stop if # response <=	OR # toxicity >=
12	0	6
27	3	10

Based on Table 10, we will perform the interim analysis when the number of evaluable patients reaches 12. When the total number of evaluable patients reaches the maximum sample size of 27, we reject the null hypothesis and conclude that the treatment is acceptable if the number of responses in the efficacy

endpoint are > 3 , and the number of toxicities are < 10 ; otherwise we conclude that the treatment is unacceptable.

Below are the operating characteristics of the design based on 10000 simulations using the BOP2 web application, which is available at <http://www.trialdesign.org>.

Table 15. Operating characteristics of BOP2 design

Pr(Eff)	Pr(Tox)	Pr(Eff & Tox)	Early stopping (%)	Claim acceptable (%)	Sample size
0.1	0.4	0.04	51.51	7.58	19.3
0.3	0.2	0.08	3.67	92.27	26.4
0.4	0.1	0.06	0.28	99.61	27.0
0.3	0.5	0.20	61.65	5.40	17.8
0.1	0.1	0.03	28.11	26.04	22.8

The Investigator is responsible for completing safety/efficacy summary reports and submitting them to the IND office Medical Affairs and Safety Group for review and approval. These should be submitted as follows:

Lead-In Phase: After the first 3 evaluable patients, complete 6 weeks of study treatment, and every 3 evaluable subjects thereafter, IND Office approval must be obtained prior to advancing/changing dose levels.

Phase II: After the first 12 evaluable subjects, and again after the first 27 evaluable subjects complete the first cycle of the combination treatment.

A copy of the cohort summary should be placed in the Investigator's Regulatory Binder under "sponsor correspondence".

10. ETHICAL AND REGULATORY REQUIREMENTS

10.1 ETHICAL CONDUCT OF THE STUDY

The study will be performed in accordance with ethical principles that have their origin in the Declaration of Helsinki and are consistent with ICH/GCP, and applicable regulatory requirements Patient data protection.

10.2 ETHICS AND REGULATORY REVIEW

This study will be subject to local IRB and federal oversight.

10.3 INFORMED CONSENT

All participants must be provided a consent form describing this study and providing sufficient information for participants to make an informed decision about their participation in this study. The formal consent of a participant, using the IRB approved consent form, must be obtained before the participant is involved in any study-related procedure. The consent form must be signed and dated by the participant or the participant's legally authorized representative, and by the person obtaining the consent. The participant must be given a copy of the signed and dated consent document. The original signed copy of the consent document must be retained in the medical record or research file.

10.4 CHANGES TO THE PROTOCOL AND INFORMED CONSENT FORM

This protocol, the proposed informed consent and all forms of participant information related to the study (e.g., advertisements used to recruit participants) and any other necessary documents must be submitted, reviewed and approved by the IRB, Aravive, and AstraZeneca. Any changes made to the protocol must be submitted as amendments and must be approved by the IRB and Aravive and AstraZeneca prior to implementation. Any changes in study conduct must be reported to the IRB, Aravive, and AstraZeneca.

11. STUDY MANAGEMENT

11.1 MONITORING OF THE STUDY

The study will be monitored by the M.D. Anderson IND office and a protocol specific monitoring plan will be followed. We will monitor unacceptable toxicity (defined as grade 3 or greater treatment-related AEs or discontinuation of the study regimen due to side effects) independently in each monotherapy treatment arm and in subsequent combination treatment, guarding against an unacceptable toxicity rate of 40% or higher (based on published studies employing combination of other Anti-PD1/PDL1 agents), using the methods of Thall et al.[64].

